6.2 Discontinuation of the Site

If an investigator intends to discontinue participation in the study, the investigator must immediately inform the Sponsor.

6.3 Discontinuation of the Study

The Sponsor may terminate this study prematurely, either in its entirety or at any study site, for reasonable cause provided that written notice is submitted in advance of the intended termination. Advance notice is not required if the study is stopped due to safety concerns. If the Sponsor terminates the study for safety reasons, the Sponsor will immediately notify the investigator and subsequently provide written instructions for study termination.

7 STATISTICAL METHODOLOGY

The statistical analysis will be coordinated by the responsible biostatistician of Astellas. A Statistical Analysis Plan (SAP) will be written to provide details of the analysis, along with specifications for tables, listings and figures to be produced. The SAP will be finalized before the database soft lock at the latest. Any changes from the analyses planned in SAP will be documented in the Clinical Study Report (CSR).

Prior to Database Lock, a Final Review of Data and TLFs Meeting will be held to allow a review of the clinical trial data and to verify the data that will be used for analysis set classification. If required, consequences for the statistical analysis will be discussed and documented. A meeting to determine analysis set classifications may also be held prior to database lock.

In general, all data will be summarized with descriptive statistics (number of subjects, mean, standard deviation, minimum, median and maximum) for continuous endpoints, and frequency and percentage for categorical endpoints. Kaplan-Meier estimates will be used to estimate medians and provide figures for time-to-event data (e.g., rPFS, time to PSA progression, and time to first use of a subsequent antineoplastic therapy).

7.1 Sample Size

Prior clinical trials data in the post-chemo setting have shown the following median rPFS for subject randomized to initial placebo, placebo+prednisone, or mitoxantrone+prednisone therapy:

- o AFFIRM: Placebo = 2.9 months
- o COU-301: Placebo + Prednisone = 3.6 months
- TROPIC: Mitoxantrone + Prednisone = 1.4 months

With a sample size of 40 subjects and an assumed median rPFS of 4 months for the therapy defined in this single-arm study, approximately 34 events are expected over a 12-month accrual and 12-month minimum follow-up. Further assuming uniform accrual, 10% loss to follow-up, and an exponential distribution for the rPFS event times, the expected lower bound of the 90% confidence interval for the median is approximately 2.5 months based upon simulations.

7.2 Analysis Set

Detailed criteria for analysis sets will be laid out in Classification Specifications and the allocation of subjects to analysis sets will be determined prior to database hard-lock.

7.2.1 Full Analysis Set (FAS)

The full analysis set will consist of all subjects who are enrolled, receive at least one dose of study drug, and have at least one post baseline evaluation. This will be the primary analysis set for efficacy analyses.

7.2.2 Per Protocol Set (PPS)

Not applicable.

7.2.3 Safety Analysis Set (SAF)

For the statistical summary of the safety data, the safety analysis set (SAF) will be used. The SAF consists of all subjects who took at least one dose of study medication, and will be used for safety analyses.

7.2.4 Biomarker Analysis Set (BAS)

The Biomarker analysis set (BAS) consists of the subset of the FAS population for which biomarker data are available to facilitate derivation of at least one of the correlative biomarkers.

7.3 Demographics and Other Baseline Characteristics

Demographics and other baseline characteristics will be summarized by treatment group for the SAF. Other baseline characteristics will include baseline disease severity measures and prior prostate cancer therapies. Descriptive statistics will include number of subjects, mean, standard deviation, minimum, median and maximum for continuous endpoints, and frequency and percentage for categorical endpoints.

7.4 Analysis of Efficacy

The primary efficacy analysis will be conducted on the FAS.

7.4.1 Analysis of Primary Endpoint

7.4.1.1 Primary Analysis

The primary efficacy endpoint, rPFS, will be analyzed using Kaplan-Meier methodology to account for censored outcomes (i.e. no observation of rPFS event within the study follow-up period).

Ninety percent (90%) confidence interval will be provided for the median rPFS.

7.4.1.2 Secondary Analysis

Not applicable.

7.4.1.3 Subgroup Analysis

The analysis described in Section 7.4.1.1 may be repeated in subsets defined by baseline characteristics such as prior treatment, prior response to enzalutamide, biomarkers, etc. In addition, multivariable analyses may be conducted using multivariable analyses. This analysis will be conducted using the FAS.

7.4.2 Analysis of Secondary Endpoints

The overall survival rate at 1 year will be estimated via Kaplan-Meier methodology with censoring defined by the time of last contact with the subject for those subjects who do not have a reported death. This analysis will be repeated in each subset defined by prior treatment with exposure.

For patients with PSA declines, the PSA progression date is defined as the date that a $\geq 25\%$ increase and an absolute increase of $\geq 2~\mu g/L$ (2 ng/mL) above the nadir is documented, which is confirmed by a second consecutive value obtained 3 or more weeks later. For patients with no PSA declines, the PSA progression date is defined as the date that a $\geq 25\%$ increase and an absolute increase of $\geq 2~\mu g/L$ (2 ng/mL) above the baseline is documented, which is confirmed by a second consecutive value 3 or more weeks later. The time to PSA progression will then be estimated via Kaplan-Meier methodology with censoring defined by the time of the last available PSA measure. This analysis will be repeated in each subset defined by prior treatment with exposure.

The proportion of subjects achieving a maximum PSA decline from baseline of at least 30% (PSA30), 50% (PSA50), and 90% (PSA90), respectively, and having an objective response will provided along with 90% confidence intervals. Analyses for PSA response rates will include all subjects with at least one post-baseline PSA measure. Analysis for objective response will include all subjects with measurable disease at baseline. These analyses will be repeated in each subset defined by prior treatment with exposure.

The time to first use of a subsequent antineoplastic therapy will be estimated via Kaplan-Meier methodology with censoring defined by the time of last contact with the subject for those subjects who do not have a reported use of antineoplastic therapy. This analysis will be repeated in each subset defined by prior treatment with exposure.

The analysis described in Section 7.4.1.3 will be repeated for secondary endpoints as appropriate.

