Samples for PSA will be collected and analyzed at the site's local laboratory. PSA testing will be performed at the Screening Visit, Week 1 (Baseline), Week 9, Week 13, Week 17, Week 21, Week 25, at subsequent 12 week intervals, and at the Safety Follow-up visit 30 days after last dose.

The PSA test performed at the Screening Visit does not need to be repeated on Day 1 if the Day 1 visit occurs within 72 hours of the Screening Visit.

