7.8 Interim Analysis (and Early Discontinuation of the Clinical Study)

An interim efficacy analysis will be conducted 13 weeks after enrollment of the 40th subject to report on PSA response rates.

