6.1.2 Secondary Efficacy Endpoints

Time to PSA Progression

For patients with PSA declines, the PSA progression date is defined as the date that a $\geq 25\%$ increase and an absolute increase of $\geq 2 \mu\text{g/L}$ (2 ng/mL) above the nadir is documented, which is confirmed by a second consecutive value obtained 3 or more weeks later.

For patients with no PSA declines, the PSA progression date is defined as the date that a $\geq 25\%$ increase and an absolute increase of $\geq 2 \mu\text{g/L}$ (2 ng/mL) above the baseline is documented, which is confirmed by a second consecutive value 3 or more weeks later. Baseline is defined as last PSA measurement prior to first dose.

Time to PSA progression is defined as the PSA progression date minus date of first dose + 1, which will be censored in the following scenarios:

- If patient does not have any PSA progression, it will be censored at last PSA sample date.
- If patient does not have post baseline PSA assessment, it will be censored at Day 1.
- If patient took any new anti-cancer therapy before any PSA event, the time to PSA progression will be censored at the PSA sample date prior to the date of new anti-cancer therapy.

Overall Survival Rate at 1 Year

Overall Survival is defined date of death due to any cause minus date of first dose +1. If a patient has not died, overall survival is censored at the last known alive date.

The last known alive date will be derived based on the maximum of last known alive dates in the survival follow up CRF page, last visit, or last SAE onset date.

Overall survival rate at 1 year is defined as the corresponding Year 1 (Day 365) Kaplan-Meier estimate on survival curve.

Time to first use of a subsequent antineoplastic therapy

Time to first use of a subsequent antineoplastic therapy is defined as date of the first systemic antineoplastic therapy minus first dose date +1. If a patient has not started the antineoplastic therapy, the time to event analysis is censored at the last dose date of study medication.

PSA response

PSA response is defined in below categories:

- PSA30 (maximum decline of $\geq 30\%$ decline from baseline at lowest post baseline)
- PSA50 (maximum decline of $\geq 50\%$ decline from baseline at lowest post baseline)
- PSA90 (maximum decline of $\geq 90\%$ decline from baseline at lowest post baseline)

Objective response rate

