Objective Response Rate (ORR) is the proportion of patients whose best overall response is Complete Response (CR) or Partial Response (PR) per RECIST 1.1. Only patients with measurable disease at baseline will be included in the analysis of ORR.

Best Overall Response is derived based on the time point response information on the CRF according to RECIST criteria for both subjects with measureable and non-measureable disease:

- CR
- PRNon Cr/Non Pd
- SD
- NE

The derivation of BOR is implemented using SAS based solely on investigator assessed information across all timepoints. Confirmation of response is not required according to the protocol.

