7.8 Subgroups of Interest

rPFS, time to PSA progression, and PSA30 will be analyzed for the subgroups defined on the basis of the categorized variables at baseline listed below:

- Ensure to capture subgroups from AFFIRM, plus the following groups of interest to this study
- CTC detected (yes vs no)
- AR-v7 (yes vs no)
- Prior abiraterone
- PSA90 on prior enzalutamide
- Prior enzalutamide treatment duration > median
- PSA50 on prior docetaxel
- Prior docetaxel treatment duration \geq median

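### PSA30/50/90 rest on each man's single lowest PSA with no confirming value, so as evidence of activity in a single-arm study PSA30, and PSA50 less so, can be overstated by measurement noise

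*Protocol*

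**What the plan says.** Protocol 7.4.2 gives the response endpoint as "The proportion of subjects achieving a maximum PSA decline from baseline of at least 30% (PSA30), 50% (PSA50), and 90% (PSA90" thresholds. SAP 6.1.2 makes the rule explicit: each category is a "decline from baseline at lowest post baseline" value. The comparator is one measurement: "Baseline is defined as last PSA measurement prior to first dose".

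For PSA progression, the same two sections count a rise only if it is one "which is confirmed by a second consecutive value obtained 3 or more weeks later". No section asks for the equivalent for a decline. The SAP sentence "Confirmation of response is not required according to the protocol" sits under objective response and concerns RECIST best overall response; the SAP makes no such statement about PSA.

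Protocol 5.3.2 sets the draws at local laboratories: "PSA testing will be performed at the Screening Visit, Week 1 (Baseline), Week 9, Week 13, Week 17, Week 21, Week 25", then every 12 weeks and at safety follow-up.

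The rates are used in several places:
- The interim (Protocol 7.8) is run "to report on PSA response rates"; SAP 7.10 keeps that report internal and makes no adjustment.
- SAP 7.8 states that "rPFS, time to PSA progression, and PSA30 will be analyzed for the subgroups" it lists.
- SAP 7.4.3 relates AR-V7 status to all three PSA thresholds.
- SAP 7.4.2 attaches exact 90% Clopper-Pearson limits, with no threshold or test.

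**The concern.** The lowest of several noisy values is compared with one noisy baseline. A low draw or a high baseline can carry a man past 30% without any real fall, and the chance grows with the number of draws. Men who stay on study longer are therefore more likely to be counted, for a reason that is partly mechanical. A Clopper-Pearson interval covers sampling error, not this shift.

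There is no control arm to show how often the rule makes responders by chance. PSA response is the only result named for the interim. PSA30, the threshold closest to the noise, is the only response rate listed for the SAP 7.8 subgroups. At the interim, the last men enrolled have at most the Week 9 and Week 13 values under the protocol schedule, while early enrollees still on study may have five or more.

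**Working it through.** **The plan's own figures.** The documents state no expected PSA30/50/90 rate, so there is no PSA figure to reproduce. The sizing figure does reproduce: 40 × 0.90 × the mean over entry time u in 0-12 months of {1 − exp[−(ln 2/4)(24 − u)]} = 34.1, against 34 stated. It bears here only through the number of draws. With a 4-month median, the share progression-free at Week 25 (168 days, 5.52 months) is exp[−(ln 2/4) × 5.52] = 0.38, so five draws will be more than many men have.

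**Inputs.** From the documents: one baseline value, five post-baseline draws to Week 25 (two for the last enrollees at the interim), 40 men. Assumed, because the documents do not give it: independent normal error on log PSA with SD s = 0.10, 0.15 or 0.20 (roughly 10-20% variability) at baseline and at each draw, with a constant true ratio to baseline.

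**Direction.** If two consecutive values meet a threshold, the lowest value meets it too. From the same draws the unconfirmed rate can never be below the confirmed rate. This needs no assumption.

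**Size for one man.** For a flat PSA, one draw gives P = Φ(ln 0.70/(s√2)), with ln 0.70 = −0.357: Φ(−2.52) = 0.6%, Φ(−1.68) = 4.6%, Φ(−1.26) = 10.4%. For the lowest of k draws, P = E[1 − {1 − Φ(ln 0.70/s + Z)}^k], Z standard normal; k = 5 gives 2.4%, 15.6% and 30.1%. Confirmed rates, and the rows with a true fall, come from simulating the same model with 1,000,000 men per setting.

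| True change | Draws | PSA30 unconfirmed, s = 0.10 / 0.15 / 0.20 | PSA30 confirmed |
|---|---|---|---|
| none | 5 | 2.4 / 15.6 / 30.1% | 0.2 / 3.0 / 8.4% |
| none | 2 | 1.1 / 8.2 / 17.3% | 0.1 / 1.1 / 3.4% |
| 20% fall | 5 | 44.0 / 58.7 / 65.8% | 15.8 / 26.5 / 33.1% |
| 40% fall | 5 | 98.9 / 96.7 / 94.8% | 92.4 / 84.0 / 78.2% |
| 40% fall | 2 | 94.9 / 89.1 / 84.9% | 77.4 / 64.2 / 56.6% |

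The first three rows are false PSA30 responses; the last two are true ones. With flat PSA and five draws, false PSA50 reaches at most about 3% and false PSA90 is 0%. With PSA truly rising and variability of 10-20%, unconfirmed false PSA30 over five draws is 0.0-0.3% (doubling in 3 months) and 0.0-2.9% (6 months).

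**Size for a cohort.** Three assumed populations were used, with log true ratio normal: mean 0.3, SD 0.7; mean 0.1, SD 0.6; mean 0, SD 0.8. Their true PSA30 rates are about 17%, 22% and 33%. Over 3 or 5 draws and 10-20% variability:
- Unconfirmed PSA30 minus the true rate: +3.6 to +13.9 points.
- Confirmed PSA30 minus the true rate: −1.6 to +3.0 points.
- Unconfirmed minus confirmed PSA30: 4.1 to 11.3 points, or 0.041 × 40 = 1.6 to 0.113 × 40 = 4.5 men.
- Unconfirmed minus confirmed PSA50: 2.5 to 7.9 points.

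A second set of continuous populations gave about −4 to +3 points (confirmed) and +2 to +15 points (unconfirmed) around the true PSA30 rate. For scale, 10 of 40 responders has an exact 90% interval of 14% to 39%.

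**The case against.** Maximum decline is the endpoint, worded alike in the objectives, endpoints and analysis sections of both documents. Confirming progression fixes an event date; best PSA decline is a different quantity. A reader might infer from the asymmetry that the plan contradicts itself. It does not, and objective response is openly unconfirmed too. The rates are descriptive, the interim is internal with no decision rule, and a waterfall plot already shows each man's maximum decline. All of this stands.

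The size rests on assumptions. The model holds the true ratio constant, so it treats any brief real nadir as noise, and much of the cohort excess comes from men assumed to lie near the 30% line. That stands as well.

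Confirmation has its own bias. For a true 40% fall and two draws it misses 100 − 77.4 = 22.6% to 100 − 56.6 = 43.4% of true responders. From two draws to five, the unconfirmed rate for these men moves from 95/89/85% to 99/97/95%, but the confirmed rate moves from 77/64/57% to 92/84/78%. A confirmed rate is thus less comparable between interim and final, and it too depends on time on study. This defeats any proposal to make confirmed PSA30 the subgroup or interim measure in place of the prespecified one. It does not count against showing both.

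**Conclusion.** The point holds as a limit on interpretation, not as an error in the definition. That the unconfirmed rate is at least the confirmed rate is certain. The gap is not fixed by the documents: at an assumed 10-20% within-man variability, false PSA30 in a man with flat PSA and five draws is about 2-30% unconfirmed and 0.2-8% confirmed, and the gap in the assumed mixed populations is about 4 to 11 points, or 2 to 5 of 40 men. PSA50 is affected less; PSA90 and fast-rising PSA hardly at all.

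Two stronger readings are tempting. One is that PSA30 is overstated as a matter of fact; the documents give neither the PSA noise level nor the trajectories needed to say so, and never present the rate as a sustained response. The other is that PSA30 is the only response rate examined in any subset; that is true of SAP 7.8, but Protocol 7.4.2 repeats all the response rates by prior treatment.

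**What to change.** Keep the maximum-decline PSA30/50/90 rates, the subgroup analyses and the waterfall plot as prespecified, and label those rates unconfirmed.

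In Protocol 7.4.2 and SAP 6.1.2 and 7.4.2, add confirmed PSA30/50/90: the threshold is met at two consecutive post-baseline values at least 3 weeks apart. Give exact 90% intervals and show these rates beside the unconfirmed ones at the final analysis, in the SAP 7.8 PSA30 subgroups and at the interim. Do not replace the unconfirmed rates.

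The cost is SAP wording, matching protocol wording and one derivation. PSA is already drawn every 4 weeks from Week 9 to Week 25, so no sample is added. State the downside with the results: confirmed rates are lower and miss some true responders near the threshold, above all men with only Weeks 9 and 13 at the interim, and declines first seen at the last PSA or after Week 25, when scheduled draws are 12 weeks apart. Interim and final confirmed rates are therefore not directly comparable.

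The SAP flow chart marks a Week 5 PSA that the protocol schedule lacks. The two schedules must be reconciled, because the number of draws enters both rates.

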DDI studies in healthy subjects showed that concomitant medications can affect exposure to enzalutamide. Coadministration of gemfibrozil (a strong CYP2C8 inhibitor) increased the composite AUC of enzalutamide plus N-desmethyl enzalutamide by 2.2-fold; therefore, strong CYP2C8 inhibitors are to be avoided. If coadministration with a strong CYP2C8 inhibitor is necessary, the dose of enzalutamide is to be reduced to 80 mg once daily. Coadministration of itraconazole (strong CYP3A4 inhibitor) increased the composite AUC of enzalutamide plus N-desmethyl enzalutamide by 1.3-fold; as this small change is not clinically meaningful; no starting dose adjustment is needed when coadministering enzalutamide with CYP3A4 inhibitors.

Coadministration of rifampin (moderate CYP2C8 inducer and strong CYP3A4 inducer) decreased the composite AUC of enzalutamide plus N-desmethyl enzalutamide by 37%.

In vitro data indicate that enzalutamide and its major metabolites are not substrate for human P-glycoprotein (P-gp); enzalutamide and N-desmethyl enzalutamide are inhibitors for P-gp.

In vitro data also show that enzalutamide and N-desmethyl enzalutamide do not appear to be substrate for human breast cancer resistance protein (BCRP), however, enzalutamide and N-desmethyl enzalutamide are inhibitors of BCRP at clinically relevant concentrations.

Two phase III randomized trials have demonstrated significant activity of enzalutamide in men with mCRPC. In the phase III AFFIRM trial [Scher et al, 2012], 1199 men with prior chemotherapy exposure who were randomly assigned to receive enzalutamide versus placebo, a statistically significant improvement in OS of 18.4 versus 13.6 months was detected with enzalutamide (HR, 0.63; 95% CI, 0.53 to 0.75; P < .001). Radiographic PFS (rPFS) was 8.3 versus 2.9 months (HR, 0.40; P < .001), PSA response was 54% versus 2% (P < .001), time to PSA progression was 8.3 versus 3.0 months (HR, 0.25; P < .001), and time to first skeletal-related event was 16.7 versus 13.3 months (HR, 0.69; P < .001), all in favor of enzalutamide. Overall QOL benefit was observed in 43% versus 18% (P < .001) of patients receiving enzalutamide compared with placebo, whereas fatigue, diarrhea, and hot flushes were more common with enzalutamide. Five patients (0.6%) experienced seizures in the enzalutamide group.

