7.4.2 Analysis of Secondary Endpoints

Overall Survival, time to PSA progression, and time to first use of a subsequent antineoplastic therapy will be analyzed in the same manner as the primary endpoint.

PSA response rate (PSA30, PSA50, and PSA90) and objective response rate along with exact 90% confidence interval (Clopper-Pearson) will be calculated.

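### Time to first subsequent antineoplastic therapy is estimated by Kaplan-Meier with untreated deaths censored, so any such death makes next therapy look more frequent and earlier than it is

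*Protocol*

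**What the plan says.** Protocol 7.4.2 specifies the estimator: "The time to first use of a subsequent antineoplastic therapy will be estimated via Kaplan-Meier methodology". It censors at last contact "for those subjects who do not have a reported use of antineoplastic therapy". Patients who die without further therapy fall in that group, and nothing excepts them.

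SAP 6.1.2 defines the event as therapy start alone: "Time to first use of a subsequent antineoplastic therapy is defined as date of the first systemic antineoplastic therapy minus first dose date +1". It then sets a different censoring date: "If a patient has not started the antineoplastic therapy, the time to event analysis is censored at the last dose date of study medication".

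SAP 7.4.2 says that "time to first use of a subsequent antineoplastic therapy will be analyzed in the same manner as the primary endpoint", which means a Kaplan-Meier curve, a median and a two-sided 90% confidence interval (SAP 7.4.1). Protocol 7 describes the intended output in general terms: "Kaplan-Meier estimates will be used to estimate medians and provide figures for time-to-event data".

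The SAP counts death as an event in rPFS, composite PFS and overall survival, but not here. For this endpoint neither document names death as a competing event, plans a cumulative incidence, or adds a sensitivity analysis.

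**The concern.** A patient who has died cannot start another therapy. When Kaplan-Meier censors him, it treats him as someone who would later have started at the same rate as the patients still followed. One minus the curve then describes a population in which nobody dies. A reader of the clinical study report will take the curve and the median as the share of patients who went on to further treatment and when they did so.

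Choosing between last contact and last dose as the censoring date does not remove the problem, because untreated deaths are censored under both rules. At stake is the accuracy of one named secondary endpoint: how long re-treatment defers the next line of therapy, and for how many patients.

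**Working it through.** **The plan's own figure.** No target or expected value is given for this endpoint. The one design figure that can be checked is the roughly 34 rPFS events in Protocol 7.1. With an exponential median of 4 months and follow-up uniform over 12 to 24 months, P(event) = 0.947, and 40 × 0.947 × 0.9 = 34.1. It reproduces, but it does not bear on this point.

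**Inputs.**
- Event, estimator and censoring rules: Protocol 7.4.2, SAP 6.1.2 and SAP 7.4.2.
- Mortality scale: Protocol 1.2 reports, for an earlier trial after chemotherapy, "a statistically significant improvement in OS of 18.4 versus 13.6 months was detected with enzalutamide". These medians serve only as the high-mortality end of a range.
- Not in the documents, therefore assumed: median to new therapy in the absence of death, 4 to 12 months; median to death before new therapy, 13.6 to 60 months; independent constant hazards.

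**Formulas.** Let a be the hazard of new therapy and b the hazard of death before it.
- Kaplan-Meier with deaths censored estimates 1 − exp(−aT).
- The proportion who have actually started by T is the cumulative incidence, a/(a+b) × [1 − exp(−(a+b)T)].
- The time at which half have started is −ln[1 − 0.5(a+b)/a]/(a+b).

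The first expression exceeds the second whenever b > 0.

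**Worked case.** Medians of 6 and 18.4 months give a = ln2/6 = 0.1155 and b = ln2/18.4 = 0.0377. At 12 months, 1 − KM = 1 − exp(−1.386) = 75.0%. The cumulative incidence is 0.754 × [1 − exp(−1.838)] = 0.754 × 0.841 = 63.4%. Half have started by 1.088/0.1532 = 7.1 months, against a Kaplan-Meier median of 6.0.

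**Range** (months; differences taken before rounding):

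| Median to therapy, no deaths (= KM median) | Median to death before therapy | 1 − KM at 12 | Cumulative incidence at 12 | Excess, points | Time half have started |
|---|---|---|---|---|---|
| 4 | 13.6 | 87.5% | 72.0% | 15.5 | 4.6 |
| 4 | 60 | 87.5% | 83.5% | 4.0 | 4.1 |
| 6 | 13.6 | 75.0% | 60.0% | 15.0 | 7.7 |
| 6 | 60 | 75.0% | 71.1% | 3.9 | 6.3 |
| 8 | 13.6 | 64.6% | 50.9% | 13.8 | 11.5 |
| 8 | 60 | 64.6% | 61.1% | 3.6 | 8.5 |
| 12 | 13.6 | 50.0% | 38.7% | 11.3 | 26.1 |
| 12 | 60 | 50.0% | 47.1% | 2.9 | 13.2 |

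The excess is about 3 to 16 points at 12 months and, by the same formulas, 6 to 27 points at 24 months.

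**Effect of the SAP's censoring date.** The formulas above match the protocol's last-contact rule. The SAP's last-dose rule was compared with it by simulation, assuming a median time on drug of 4 months, a median gap from stopping drug to next therapy of 1 to 4 months, and a median time to death of 13.6 or 18.4 months:

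| | Starting by 12 months | Excess, points | Median, months |
|---|---|---|---|
| True | 45–69% | – | 6.5–14.6 |
| Protocol rule (last contact) | 61–83% | 13–19 | 5.6–9.7 |
| SAP rule (last dose) | 69–84% | 15–25 | 5.5–8.8 |

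The SAP rule does worse because a non-starter leaves the risk set when he stops drug. His untreated time off drug, and his death if it follows, no longer count. A starter is kept until his therapy date. This simulation uses only the high-mortality end of the range, so it compares the two rules and does not forecast the trial.

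**The case against.** Several objections have force.

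- **No rate of untreated death is given.** A reader might infer that many of these patients die without another line of therapy. The documents do not say so. If nobody died untreated, the bias under the protocol's rule would be zero.
- **The overall survival medians overstate the relevant hazard.** They include deaths after subsequent therapy and come from a trial of first exposure to enzalutamide. Taken as constant hazards they imply 20% to 26% dead by 6 months, although inclusion criterion 9 asks for an estimated life expectancy of at least 6 months. A reader might take the 11 to 15 points that these medians give at a 6-month median to therapy as the expected bias. That is only the upper part of the range.
- **No fixed-time proportion is planned here.** The planned output is the curve and the median. The excess in percentage points arises when someone reads a proportion off the curve. The median is affected directly, by anything from 0.1 month to many months.
- **Kaplan-Meier with deaths censored has a legitimate use.** It describes the rate of starting therapy among those alive and untreated. The plan does not offer it with that caveat.
- **Precision is low.** With 40 patients, the 90% half-width for a proportion near 50% is 1.645 × √(0.25/40) = 13 points, similar to the larger biases. The interval quantifies sampling error only and would not reveal a systematic shift.

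These points limit the size and the importance. None reverses the direction.

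**Conclusion.** The point holds as to direction. Both documents censor untreated deaths by implication, since all non-starters are censored without exception; neither says so outright. Whenever such a death occurs, the Kaplan-Meier curve overstates the proportion starting new therapy and its median is too early.

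The size rests on assumed, independent constant hazards. Over the range tried, 3 to 16 points at 12 months is about 1 to 6 of 40 patients (40 × 0.03 = 1.2; 40 × 0.16 = 6.4). The SAP's last-dose rule conflicts with the protocol's last-contact rule and enlarges the error.

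A reader might also infer that the trial's main conclusion is at risk. It is not: rPFS already counts death as an event, and this endpoint is secondary and descriptive, with no test or decision rule attached. The change is worth making because it is cheap, not because the trial depends on it.

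**What to change.** In SAP 6.1.2 and 7.4.2:

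1. Make the main estimate the cumulative incidence of first subsequent therapy, with death before therapy as a competing event (Aalen-Johansen). Give 90% confidence intervals at, for example, 6 and 12 months, and the time at which incidence reaches 50%, if it does.
2. Censor patients who are alive and untreated at last contact, as in Protocol 7.4.2, and delete the last-dose rule. Without this step, deaths after drug is stopped would still be lost.
3. Optionally add Kaplan-Meier for therapy or death, labelled as a different quantity. It gives earlier medians: 4.5 months in the 6 / 18.4-month case, from ln2/(0.1155 + 0.0377).
4. State that the estimator departs from the Kaplan-Meier method named in Protocol 7.4.2, and why.

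No new data are needed: Protocol 5.3.4 already follows survival and subsequent therapies every 12 weeks for all subjects. The cost is SAP wording, a small programming change and a lower, less favourable reported proportion. Sample size and error rates do not change.
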